Patients will be recruited from the inpatient services and outpatient clinics of the University of Oklahoma Health Sciences Center. A meeting with all study personnel to review the study protocol will be held before initiation of the study, as well as every 3-6 months, depending on study progress. Informed consent will be obtained prior to enrollment in the study. The randomization schedule will be implemented with the use of concealed envelopes and it will be stratified by sex. Blocked randomization will be used to decrease the chance of imbalances in the two groups over time.

After informed consent and screening procedures are completed, all patients will undergo noninvasive continuous ECG monitoring for 2 weeks to evaluate their AF burden (the percent of time spent in AF) using an adhesive waterproof continuous monitoring patch (Zio[®] Patch). The Zio[®] Patch (iRhythm Technologies, Inc) is an FDA approved, single-lead, lightweight, 14-day ambulatory ECG adhesive patch monitor. The patch is well tolerated and allows significantly longer continuous monitoring than a regular Holter monitor, leading to an improved AF detection rate ³⁴. After the 2-week monitoring period, patients will be randomly assigned (1:1) to active or sham LLTS. Patients will be blinded to the treatment allocation, and every effort will be made to conceal from the study personnel the nature of the intervention in each study arm. Blinding of the patients will be accomplished by having a sham control arm, in which stimulation will be delivered to a different site (the ear lobe), devoid of vagal innervation ³⁵. By doing so, all patients will be aware that they are receiving stimulation, but they will not be told which site achieves active VN

stimulation. The patients will be requested to refrain from discussing the details of their treatment with other patients in the clinic and with the physicians, nurses and the rest of clinic staff. The clinical coordinator and a clinic physician who will not participate in any of the other study related assessments will be unblinded to the treatment allocation and will instruct the patients on the proper use of the device. These study personnel will be designated to address the patients' questions and concerns as well as to record any side effects related to the use of the device.

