Patients will be anticoagulated according to the 2014 ACC/AHA guidelines ³⁶. Specifically, patients with a CHADS2-VASc score of 1 or greater will receive anticoagulation, with either one of the new oral anticoagulants or warfarin (target INR 2-3). All other medications, including antiarrhythmic medications will be continued. The choice of antiarrhythmic medications will be left at the discretion of the treating physician. The experimental device will be used in addition to all the other medications; in other words, the device will be used only with individuals continuing drug treatment.

Patients will be enrolled in the study over 17 months and the total duration of the study will be 24 months (each patient will be followed for 7 months). During the baseline visit (after the 2 week monitoring period), a complete history and physical examination will be done by one of the investigators. Laboratory data and echocardiographic data, when available, will also be reviewed. A 5-minute ECG for HRV analysis (see below) will be performed at the same time. After the ECG is completed, 10ml of blood will be drawn for cytokine analysis (see below). Since blood draw is likely to cause an increase in the sympathetic tone, it will be performed after the ECG is completed, to avoid any interfering with HRV analysis. After the ECG and blood draw is completed (to avoid

contamination of the baseline data by stimulation), patients will be instructed on how to use the LLTS and attach the electrode pads and will be asked to repeat the process themselves under direct supervision, to ensure correct use of the device. This process will be done by a clinical coordinator and/or physician who is unblinded to random allocation.

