We intend to recruit 52 patients. Participants will be evaluated at 1, 3 and 6 months. At each follow-up visit, patients will have a brief history and physical examination, and any cardiovascular events, including symptomatic AF episodes will be recorded. In addition, the discomfort threshold for tragus stimulation will be obtained to ensure that patients are receiving adequate stimulation. At the 1 month visit, the patients will be interviewed by the unblinded physician or clinical coordinator to address any issues with LLTS administration at home, and to assess their adherence to the stimulation protocol. At the 3 and 6 month visit, patients will have a 5-minute ECG and blood drawn, as during the baseline visit. In addition, patients will undergo noninvasive continuous ECG monitoring for 2 weeks to evaluate their AF burden using an adhesive patch (Zio[®] Patch).

A schematic representation of the study design and timeline of events is shown in Figure 4.

HRV analysis: HRV is a marker of VN activity and can be easily measured by software calculating the distance between consecutive R waves on the ECG ³⁷. Importantly, measures of HRV have been inversely correlated with inflammatory cytokines (C-reactive protein, IL-6) in the general population ³⁸⁻⁴⁰. At each visit, a 5-minute ECG will be obtained for HRV analysis. ECG will be obtained in the supine position after resting for 15 minutes while heart rate, blood pressure and respiration will be monitored. All participants will be asked to avoid caffeine for 4 hours and alcohol, smoking and exercise for 12 hours prior to the visit to avoid any interfering with the results of their ECG. This test will done using a PC-Based ECG device. Analysis and interpretation of the HRV data will be performed in a blinded fashion.

Specific Aim 2: To examine the effect of intermittent (1 hour daily) LLTS on inflammatory cytokines and their gene expression in patients with paroxysmal AF over a 6-month period.

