Sample size and power calculations: For purposes of sample size calculations we have simplified the analysis to focus on the AF burden at the 6-month time point between the 2 groups. Assuming a mean±standard deviation AF burden in the control group of $28.4\pm31.2\%$ ³⁴ and a 87% reduction in the LLTS group to 3.7% (assuming a common standard deviation of 31.2%), 26 patients per group would provide 80% power to detect the specified effect sizes at a two-sided significance α level of 0.05. Approximately 30 patients with paroxysmal AF are seen in our clinics each month. Assuming that 1 out of 4 eligible patients would agree to participate in the study, we should be able to enroll the required number of patients within the proposed 17 months, allowing for 6 months of additional follow up and a final month for data analysis.

F. Gender/Minority/Pediatric Inclusion for Research

Participants will be age 21 or older. Race, minority status and gender will not affect enrollment.

[figure not shown]
G. Human participants

The study population will include 52 male/female patients with paroxysmal AF, aged 21 or older, including all races. Since AF is extremely rare in patients less than 21 years old, this age limit is not expected to affect the overall results.

Inclusion Criteria:

- 1. Male and female patients older than 21 year old
- 2. Paroxysmal AF

Exclusion Criteria:

- 1. Left ventricular dysfunction (Left ventricular ejection fraction <40%)
- 2. Significant valvular disorder (i.e., prosthetic valve or hemodynamically relevant valvular diseases)
- 3. Recent (<6 months) stroke or myocardial infarction
- 4. Severe heart failure (NYHA IV)
- 5. Left atrial dilatation (>55mm)
- 6. Recurrent vaso-vagal syncopal episodes
- 7. Unilateral or bilateral vagotomy
- 8. Pregnancy or breast feeding
- 9. Sick sinus syndrome, 2nd or 3rd degree AV block, bifascicular block or prolonged (PR>300ms) 1st degree AV block.
- 2. Identify sources of research material in the form of specimens, records or data.

The research information will consist of the AF burden and serum inflammatory cytokines at each time point specified in the protocol (see Figure 4).

- 3. Describe plans for recruitment and consent procedures to be followed.
- a. Describe the location where consent is most likely to take place (will consent be obtained while an inpatient, in the ER/ICU, will consents be mailed with follow-up meeting to discuss the consent, etc.).

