Patients will be recruited from the inpatient services and outpatient clinics of the University of Oklahoma Health Sciences Center. All candidate subjects will have the purpose of the study explained to them, including the benefits and risks and options, prior to scheduled ablation procedure, will be asked to read the consent form, and after questions have been answered, will be asked to participate. Finally, they will be asked to sign the consent form.

[figure not shown]
b. Describe provisions for recruiting non-English speaking participants.

Only English-speaking persons will be recruited. Non-English-speaking adults constitute less than 1% of the patients referred for ablation.

c. Describe measures to decrease coercion of participants (allowing adequate time to review the consent, avoid recruitment of your own private patients – or have a qualified assistant assist with the consent of these individuals, avoid recruiting employees or staff to serve as controls, etc.).

Patients will have adequate time to review the consent. Recruiting of employees or staff by the principal investigator will be avoided.

[figure not shown]
3. Describe risks and assess likelihood and seriousness.

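### The recruitment section describes ablation candidates, the rest of the plan does not, and nothing in eligibility, recording or analysis addresses an ablation before the 6-month AF-burden measurement

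*Combined protocol and SAP*

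**What the plan says.** Section G (Human participants), item 3a, opens with a general recruitment sentence: "Patients will be recruited from the inpatient services and outpatient clinics of the University of Oklahoma Health Sciences Center". The next sentence covers all candidates and places the explanation of the study "prior to scheduled ablation procedure". Item 3b justifies English-only recruitment by stating that "Non-English-speaking adults constitute less than 1% of the patients referred for ablation".

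Elsewhere the population is described differently:

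- The opening summary describes ambulatory patients with paroxysmal AF who stimulate at home for 6 months.
- Section D (Research design and Methods) describes home use and patch monitoring at baseline, 3 and 6 months. On concomitant treatment it says: "All other medications, including antiarrhythmic medications will be continued". It restricts the device to people who stay on drug treatment. It does not mention ablation.
- The Patient enrollment paragraph and the sample size paragraph in Section E base accrual on about 30 paroxysmal AF patients seen in clinic each month, not on ablation referrals.

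Neither exclusion list (Section D and Section G) has a criterion on planned ablation. The inclusion list in Section G asks only for age ("Male and female patients older than 21 year old") and paroxysmal AF. At follow-up visits "any cardiovascular events, including symptomatic AF episodes will be recorded"; ablation is not named. Section E makes AF burden at 6 months the primary outcome, analyses by intention to treat, and combines the 3- and 6-month data if the group-by-time interaction is not significant.

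**The concern.** The plan gives two pictures of who is enrolled. If the recruitment section is taken literally, the trial enrols people who already have an ablation scheduled and then measures AF burden 6 months later. The plan itself presents ablation as a treatment for AF, so an ablation in between acts on the quantity that forms the primary outcome.

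Two effects are possible. If ablation is equally common in both arms, it lowers burden in both and shrinks the difference that stimulation could produce. If its use depends on how much AF persists, for example because patients who improve cancel, it could differ by arm and bias the comparison. The 3-month data are exposed to any ablation done before that patch, and the plan may pool them with the 6-month data.

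**Working it through.** **Step 1: the text.** The general recruitment sentence appears in the same words in Sections D and G, so it is not where the conflict lies. The conflict is between the two ablation statements in items 3a and 3b and the population and accrual basis in the opening summary, Section D, Patient enrollment and Section E. The earlier acute study in Section C enrolled patients who had come for AF ablation, which is a plausible source of the wording.

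**Step 2: the plan's sample size.** Inputs from Section E: control mean 28.4, active mean 3.7, common SD 31.2, two-sided alpha 0.05, power 80%.

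- Difference: 28.4 − 3.7 = 24.7 points.
- n per arm = 2 × [31.2 × (1.960 + 0.842) / 24.7]² = 25.05, rounded up to 26. This matches the plan.
- Noncentrality with 26 per arm: 24.7 / (31.2 × √(2/26)) = 24.7 / 8.65 = 2.85. Two-sample t-test power is 79.9%.

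The sample size arithmetic is sound.

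**Step 3: dilution.** The documents give no ablation rate or timing, so the share p is an assumption. Assume also that ablated patients have the same mean burden in both arms and that the SD stays at 31.2. The intention-to-treat difference is then 24.7 × (1 − p). The last column uses the n formula from step 2.

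| Ablated in each arm | Difference (points) | t-test power, 26 per arm | n per arm for 80% |
|---|---|---|---|
| 0% | 24.7 | 79.9% | 26 |
| 10% | 22.2 | 71.2% | 31 |
| 20% | 19.8 | 61.0% | 40 |
| 30% | 17.3 | 50.0% | 52 |
| 50% | 12.4 | 28.8% | 101 |

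**Step 4: letting the SD change.** Give ablated patients a mean of 3.7 and an SD s of either 31.2 or 10 (both assumed). The variance in an arm with non-ablated mean m is (1 − p) × 31.2² + p × s² + p(1 − p) × (m − 3.7)². For p = 50% and s = 10:

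- Control: 486.7 + 50 + 152.5 = 689.2. Active: 486.7 + 50 = 536.7.
- Standard error: √[(689.2 + 536.7)/26] = 6.87.
- Normal-approximation power: Φ(12.35/6.87 − 1.96) = 44%.

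Over the two SDs, power is 72% to 76% at p = 10%, 55% to 65% at 25%, and 28% to 44% at 50%.

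**Step 5: room in accrual.** On the plan's figures, 30 × 1/4 = 7.5 willing patients per month, and 7.5 × 17 = 127.5 over 17 months, against 52 needed. An exclusion could remove up to 1 − 52/127.5 = 59% of them before 52 became unreachable.

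**The case against.** The strongest reply is that the ablation phrases are leftover text. The earlier study was done at ablation, this one is described as ambulatory, accrual rests on clinic numbers, and no ablation appears among the study visits or procedures. On that reading the fault is two stray phrases and no power loss follows from them. This is plausible and cannot be ruled out. It does not remove the need for an edit, because the recruitment section would then describe the wrong population, and an ablation during follow-up would still be unaddressed.

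Three stronger readings are tempting, and the documents do not support them:

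- A reader might infer that many patients will be ablated before the 6-month patch. The text fixes only when the study is explained. It gives no ablation date, waiting time or rate.
- A reader might infer that the recruitment sentence in Section D contradicts Section G. It is repeated there in the same words, and ablation candidates can be seen in the same clinics.
- A reader might infer that the analysis is silent on data after ablation. Intention to treat by default keeps those data in the assigned arm. What is missing is a sensitivity analysis, and a record that would make one possible.

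It is also fair that the power figures describe a simple 6-month comparison, as in the plan's own calculation. The planned model adjusts for baseline and may combine two time points.

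**Conclusion.** The inconsistency is real. The recruitment section describes candidates for ablation, the rest of the plan does not, and nothing in eligibility or event recording covers an ablation within follow-up. The primary outcome could be diluted, or biased if ablation differs by arm. The text does not show that either will happen.

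The size is conditional. For an assumed 10% to 50% ablated in each arm, no between-arm difference afterwards and a fixed SD, power falls from 80% to between 71% and 29%. The fixed SD sits towards the pessimistic side: at 50% the power could be up to about 44% if burden varies less among ablated patients. The point should be settled before enrolment, but it does not invalidate the design or the sample size calculation.

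**What to change.** 1. Reconcile items 3a and 3b of Section G with the opening summary, Section D, Patient enrollment and Section E. If the ablation wording is carried over, remove both phrases.
2. Whichever reading is right, state in both eligibility lists that patients with an ablation already scheduled before the end of the 6-month monitoring are not enrolled.
3. Record any ablation during follow-up, with its date, and report it by arm.
4. Keep the intention-to-treat analysis as primary, and add a sensitivity analysis restricted to AF burden measured before any ablation. Because this selects on an event after randomization, it should be read as supportive only.

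The cost is some wording, one eligibility line, one data field and one extra analysis. The loss of candidates should be small on the general clinic basis (about 127 willing patients against 52 needed). It would be larger, possibly most of the pool, if recruitment really is from ablation referrals, so item 1 must be settled first. These changes concern enrolment, recording and analysis, not any patient's care.
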